6.3.5 On Study Visits

Screening

- Consent
- Urine Pregnancy test for women of child-bearing potential
- Height and Weight using Tanita Scale
- EKG
- IV Insertion and OGTT
- Blood draw for anemia, kidney and liver function and thyroid test and diabetes
- Physical & Medical History
- DXA Scan

Visit 2 & 3 PET Scans

- Subject will arrive to PET Center, fasted
- Urine Pregnancy Test for women of child bearing potential
- Urine Drug Screen
- A-line and IV insertion
- Mixed Meal Test on Visit 3
- A low dose CT scan will be completed immediately before or after each PET scan.
- Up to 3-4 hour PET scan
- Collection of Blood Sampled during PET scan
- Light Lunch given to subject after PET Scan

Visits 4 & 5

HIC 2000030749

- Subject will arrive fasted to the Pierce Laboratory for measurements SNS activity
- Urine Sample Collection
- Collection of Weight
- Collection of the following: Microneurography, BP, HR
- EKG
- IV Insertion
- Blood Sample
- Measurement of skin blood flow
- Sympathetic Nervous System Activity (SNSA) measurement

Visit 1: Screening Visit
 
 -Review of Consent Form -Physical and Medical history review -Pregnancy Test (females) -EKG -Blood Work -OGTT -Body Composition 
 -Tanita Scale -DXA Scan 	
Visit 2: Whole body PET/CT
 
Imaging
 
Fasting Visit
 
 - Urine Pregnancy Test (females) - Urine Drug Screen - [¹¹C]MRB - Low dose CT scan and PET scan - Norepinephrine levels (serum) 	
Visit 4: SNSA Visit – Fasting
 
 - BP, HR, PI, HR variability - EKG - MSNA
	
Visit 3: Whole body PET/CT
 
Imaging
 
Mixed Meal Test Visit
 
 - [¹¹C]MRB - Urine Pregnancy Test (females) - Urine Drug Screen - Ingestion of mixed meal - Measurement of Energy Intake - Low dose CT scan and PET scan - Norepinephrine levels (serum) 	
Visit 5: SNSA Visit - Mixed Meal Test
 
 - Ingestion of mixed meal - BP, HR, PI, HR variability - EKG - MSNA

Abbreviations: BP=blood pressure, EKG=electrocardiogram, HR=heart rate, MSNA=Muscle sympathetic nerve activity, SNSA=Sympathetic Nervous System Activity

6.3.6 End of Study and Follow-up

Follow Up Procedures:

A member of the study team will reach out to the subject 1-2 weeks upon study completion for a brief follow-up telephone call. During this phone call, the subject will be asked how they are feeling since completing the study assessments and if they have any questions or concerns.

6.3.7 Removal of subjects

Participating in this study is voluntary. Subjects are free to choose not to take part in this study. Refusing to participate will involve no penalty or loss of benefits otherwise entitled to the subject (such as health care outside the study, the payment for health care, and health care benefits).

Subjects may withdraw permission to use and disclose health information at any time by telling the study staff or by writing to;

HIC 2000030749

[name] [name]., Ph.D.

HIC 2000030749

Yale University School of Medicine
[name]
[name]
[name]

The researchers may withdraw a subject's participation in the research if deemed necessary. The subject may be asked to withdrawal from the study if they experience significant discomfort during the procedures, become pregnant during the study intervention, are not able to follow instructions during the procedures, or are not compliant with scheduled appointments.

No new health information identifying the subject will be gathered after the date of study withdrawal. Information that has already been gathered may still be used and given to others until the end of the research study, as necessary to ensure the integrity of the study and/or study oversight.

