6.2.3 Adverse Events Definition and Reporting

1. Personnel responsible for the safety review and its frequency:

The principal investigator, [name] [name] will be responsible for monitoring the data, assuring protocol compliance, and conducting the safety reviews at the specified frequency, which must be conducted at a minimum of every 6 months (including when reapproval of the protocol is sought). During the review process, the principal investigator will evaluate whether the study should continue unchanged, require modification/amendment, or close to enrollment. Either the principal investigator, the HIC, or the RSC have the authority to stop or suspend the study or require modifications.

HIC 2000030749

2. The risks associated with the current study are deemed greater than minimal for the following reasons: (choose those that apply)

The total amount of radiation in this study is from up to 3 low dose CT scans - used to optimize the PET scan – and up to 3 injections of radioactive material (20 mCi), [11C]MRB and from a low dose CT scans used to help obtain the PET images and the DXA scan .

The average yearly background radiation in the United States is about 0.3300 mrem. The amount of additional radiation from participating in this study is about 2.307 rem. This is equal to about 7.69 years worth of natural radiation.

The amount of radiation subjects will receive in this study is below the dose guidelines established by the RIDC guidelines for research purposes. This guideline sets an effective dose limit of 5 rem per year.

Adverse effects of the radiopharmaceuticals in this study have not been reported. However, the possibility exists for a rare reaction to any of the substances or procedures to which a subject is exposed.

3. Attribution of Adverse Events:

Adverse events will be monitored for each subject participating in the study and attributed to the study procedures / design by the principal investigator [name] [name], according to the following categories:

- a.) Definite: Adverse event is clearly related to investigational procedures(s)/agent(s).
- b.) Probable: Adverse event is likely related to investigational procedures(s)/agent(s).
- c.) Possible: Adverse event may be related to investigational procedures(s)/agent(s).
- d.) Unlikely: Adverse event is likely not to be related to the investigational procedures(s)/agent(s).
- e.) Unrelated: Adverse event is clearly not related to investigational procedures(s)/agent(s).

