7.5 Data Collection

All digital data will be stored either on a secured server or on University encrypted desktops or laptops. All staff members that come into contact with the data are fully trained to the current HIPAA regulations and are informed as to the proper use of all data. Identifiable paper information is kept in locked file drawers and password protected computer files. Results are published as group data without the use of characteristics that would identify individual subjects. We quote information only by number in conference discussions, scientific reports, or publications, in order to maintain anonymity. Identifiable research data, including recruitment and screening information and code keys, are stored on a secure database located on the internal PET Center Network. The PET network is protected by a Cisco PIX firewall operated by ITS. All research data are backed up nightly to a Dell PV-136T library with 4 IBM Ultrium-TD2 tape drives using the backup software Legato Networker 7.3 from EMC. Human subjects enrolled in the study are assigned a subject-specific random identifier. Subject identifiers and the means to link the subject names and codes with the research data are stored in separate locations within the database. The software of the database limits the ability to connect the random identifier to the actual subject identification information to research team members only. Access to the database is password protected and each research team member is required to have a unique ID and password to gain access to the database. Authorized users employ their netid and authentication is performed using Yale's central authentication server. Users always access research data through the random identifier only. Direct identifiers belonging to subjects who withdraw from the study, will be stripped from the key.

The data will be stored in locked filing cabinets and on the password-protected secure database on the internal Yale University PET Center Network for at least 7 years after the close of the study, accessed only by authorized personnel. After 7 years, the data will be de-identified. Data may be kept indefinitely.

HIC 2000030749

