7.12 Data Safety Monitoring Plan

The principal investigator [name] [name]. will conduct a review of all adverse events upon completion of every study subject. The principal investigator will evaluate the frequency and severity of the adverse events and determine if modifications to the protocol or consent form are required.

Research staff will call subject 1-3 days after the PET scan to check in and address any adverse events that may have arisen post PET scan.

The study will be stopped if either of the following occur:

1) If 1 or more subjects experiences a serious adverse event (SAE), which is considered by the investigator to be possibly or probably related to the radiotracer.

HIC 2000030749

2) If 2 or more subjects experience AEs of severe intensity, which are considered by the investigator to be possibly or probably related to the radiotracer and of clinical concern.

After review of the safety data, SAEs and AEs confirmed to have been related to the radiotracer will be reported to the FDA and the appropriate regulatory committees at Yale. The study will be placed on hold until a determination is made as to whether the study may continue as written, if modifications are needed, or if the study will be discontinued.

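### Section 6.3.7 read literally stops active safety follow-up of any withdrawn subject, because the bar on new health information is neither limited to revoked permission nor given a safety exception

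*Combined protocol and SAP*

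**What the plan says.** Section 6.3.7 (Removal of subjects) deals with three things in sequence.

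- **Revoking permission.** "Subjects may withdraw permission to use and disclose health information at any time by telling the study staff" or in writing.
- **Withdrawal by the researchers.** They may end a subject's participation, and a subject may be asked to leave on grounds that include "significant discomfort during the procedures, become pregnant during the study intervention".
- **Data after withdrawal.** "No new health information identifying the subject will be gathered after the date of study withdrawal". The sentence after it keeps earlier data available: "Information that has already been gathered may still be used and given to others until the end of the research study", as needed for study integrity or oversight.

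Section 7.5 (Data Collection) adds: "Direct identifiers belonging to subjects who withdraw from the study, will be stripped from the key".

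The safety sections describe monitoring in terms of current or completing subjects. In 6.2.3, "Adverse events will be monitored for each subject participating in the study". In 7.12, the principal investigator "will conduct a review of all adverse events upon completion of every study subject". In 6.3.6, a team member will "reach out to the subject 1-2 weeks upon study completion for a brief follow-up telephone call". Sections 6.2.3 and 7.12 also provide a call one to three days after a PET scan.

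**The concern.** The bar is triggered by study withdrawal, and it follows directly after a paragraph that lists two safety-relevant reasons for withdrawal. The subjects whose later course matters most for safety are therefore among those the team is told to stop gathering information on. Removing their identifiers from the key makes later contact harder still.

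Two things are at stake. The first is documentation: whether an adverse event open at withdrawal resolved might never be recorded. The second is ascertainment of serious events. Congenital anomaly is on the serious adverse event (SAE) list in 6.2.3, and under 6.2.3 and 7.12 a single SAE judged possibly or probably tracer-related stops the study. A threshold of one depends on complete ascertainment.

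**Working it through.** The point rests on wording, so the check is to set the provisions side by side and ask whether anything restores follow-up after withdrawal.

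1. **Scope of the bar (6.3.7).** The trigger is study withdrawal. Revoked permission appears two paragraphs earlier, with withdrawal by the researchers in between. Nothing ties the bar to the first and excludes the second.
2. **Safety exception.** There is none in 6.3.7 or 7.5, nor in the adverse event, pregnancy, monitoring or discontinuation sections (6.2.2, 6.2.3, 6.5.4, 7.11, 7.12, 7.14).
3. **Other contacts.** Adverse event monitoring refers to participating subjects, and the investigator's per-subject review and the 6.3.6 call refer to completion. The post-PET call is not conditional on remaining enrolled, but it does not cover microneurography and comes too early for a pregnancy outcome. The PET Center board's monthly review and the six-monthly safety review assess events already known.
4. **Case A: open adverse event.** Section 3.2.1 puts paresthesia after microneurography at under 10% of subjects, usually lasting 2 to 10 days, and persisting up to two months in under 1%. With 40 planned subjects (5.3.1):
   - any paresthesia: 0.10 × 40 = 4, so fewer than 4 expected;
   - lasting up to two months: 0.01 × 40 = 0.4, so fewer than 0.4 expected.

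   These are ceilings before asking how many would also withdraw, which the documents do not give. The allowance of up to 10% in 6.4.2 combines dropout with poor-quality data and is not a withdrawal rate.
5. **Case B: pregnancy.** Testing is repeated on each scan day (6.2.2), and the two scans are about two weeks apart (6.3). A positive test on the second scan day can therefore occur in a woman already injected once. Her own effective dose by then, from 3.2.1, is up to 0.428 rem from tracer plus 0.625 rem from CT: 0.428 + 0.625 = 1.053 rem. This is not a fetal dose. Twenty women are planned; no pregnancy or withdrawal rate is given.
6. **Comparison with completers.** Visits fit within 8 weeks (6.3) and the last call comes up to 2 weeks later: 8 + 2 = about week 10. No follow-up to resolution or to pregnancy outcome is scheduled for them. For completers it is unscheduled but permitted; for withdrawn subjects the literal wording forbids it.

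**The case against.** The strongest reply is that the sentence is a privacy clause. Its companion sentence speaks of data being used and given to others, which echoes the earlier text on permission to use and disclose. A revocation-only reading is natural, and it stands as a possible intention. The text does not state it, and that ambiguity is what the fix removes.

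Other parts of the reply also have force. Withdrawal for discomfort or pregnancy is discretionary, so an investigator could stop procedures and keep the subject enrolled. The bar concerns identifying information, and 7.5 has users reach research data through a random identifier, so coded safety data are not clearly barred; yet active follow-up means contacting a known person. Section 7.5 does not say when the key is stripped. Passive routes remain: injury care (6.5.7) and reporting of unanticipated problems (6.2.3) could bring an event to the team if the subject returns. The consent form is not in the published text and may contain post-withdrawal contact terms.

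Two stronger readings are tempting but unsupported.

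- A reader might infer that 6.3.7 contradicts the SAE list or the stopping rule. It does not: both act on known events, and information gathered before withdrawal remains usable for oversight.
- A reader might infer that the clause is the reason such events go unfollowed. It is not the sole cause, since nothing comparable is scheduled for completers; deleting the sentence alone would add no follow-up.

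**Conclusion.** The point holds on the literal text: active follow-up of an open adverse event or a pregnancy is forbidden for withdrawn subjects, whatever the reason for withdrawal. It rests on reading the 6.3.7 bar as it is written; if only revoked permission was intended, the defect is one of drafting.

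The size is small. The expected frequency is very low and cannot be estimated from the documents. Paresthesia, the more realistic case, is a microneurography event and has no bearing on the tracer stopping rule. A missed stopping event would require a pregnancy found after a scan, withdrawal, and a listed serious outcome judged possibly or probably tracer-related. A reader might infer a material threat to the stopping rule, but the documents supply none of the rates needed to support that. No efficacy analysis is affected. This is a cheap improvement of low priority.

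**What to change.** In 6.3.7, separate stopping study procedures from revoking permission to use health information. Limit the sentence barring new health information, and the key-stripping sentence in 7.5, to subjects who revoke permission. For subjects who stop or are withdrawn without revoking it, keep the link and, with their agreement, follow adverse events open at withdrawal to resolution and any pregnancy found after a scan to outcome. Check the consent form's withdrawal terms before making the change and align them if needed.

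The cost is a few sentences of protocol text, matching consent wording, and a few extra calls by existing staff. The downside is that identifiers are kept longer for these few subjects.

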6.4 Statistical Method

6.4.1 Statistical Design

Primary endpoints: Group differences in 1) [¹¹C]MRB-binding in brown adipose tissue (BAT), white adipose tissue (WAT), skeletal muscle, and norepinephrine-rich brain regions (hypothalamus and thalamus); and 2) microneurography (muscle sympathetic nerve activity (MSNA)). Correlations between NET in the brain and peripheral NET and MSNA.

Secondary endpoints: Plasma hormone levels, heart rate, blood pressure, electrocardiogram (beat-to-beat)..

Statistical Analysis: Before statistical testing, all continuous variables will be tested for normality of distribution. Summary statistics will be computed. For between-group comparisons of patient characteristics, two sample t-test or Mann-Whitney U test will be used for continuous variables, and Fisher's exact test for categorical variables. Comparisons of repeatedly measured MSNA will be made using the mixed model analysis. Fixed factors include group and sex and their interactions. Linear contrasts comparing differences between groups or different time points within a group will be estimated.

6.4.2 Sample Size Considerations

Statistical Considerations: sample sizes of 6 per group (normal BMI x obesity, and women x men) will achieve 90% power to detect a between-group difference. To account for up to 10% missing data due to drop out or poor-quality data, we will need to enroll a total of 40 subjects (10 per group) for this study.

Fasting: A Power analysis was performed based on previous study published from our group in lean and obese female individuals: (lean 1.15 ± 0.19 vs obese 0.80 ± 0.12 BAT DVR, $p = 0.004$; two-sided independent sample t-test)². In our previous cross-sectional comparison,

HIC 2000030749

using the mean and standard deviations between lean and obese individuals, we expect an effect size of $d=2.20$ and with a power of 0.90, to account for possible smaller differences in males, we need 6 individuals per group. For reference, $d=2.20$ and 0.80 power would be 5 per group.

MMT: Postprandial whole-body energy expenditure per fat free mass (FFM) differences were shown for low-BAT (32 ± 2 kcal/day/kg FFM) and high-BAT (37 ± 2 kcal/day/kg FFM)⁴⁵. Based on these data, we can calculate an effect size of $d=2.50$. With a power of 0.80 required, we will need 8 individuals (4 per group) determine EE differences between low- and high-BAT individuals. Increasing the power to 0.95 will increase the number of individuals to 12 (6 per group). Due to the technical challenges of performing microneurography on multiple occasions in obese women, we overestimate and account for $\sim 10\%$ failure rate, so we will recruit 10 subjects per group.

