4.3 Secondary Objectives (if applicable)

The secondary objectives of this study are: 1) to evaluate whether gender differences affect peripheral SNS in healthy normal weight and obese men and women in adipose tissue (WAT and BAT) and muscle (resting/fasting); 2) To investigate the relationship between peripheral and central SNS activity in obesity, by correlating SNS activity in peripheral tissues (WAT, BAT, and muscle) and brain; and 3) To investigate NET CNS and peripheral SNS activity before and after a high carbohydrate mixed meal in lean and obese men and women.

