High Carbohydrate Mixed meal test (MMT): Two weeks after visit 2, participants will come to the PET Center after a 10-hour overnight fast. A nurse will insert an intravenous (IV) catheter and subjects will ingest a liquid meal (65% CHO, 20% fat, and 15% protein, equal to 40% of daily energy expenditure, per ~16 ounces) to be prepared by the Metabolic Kitchen located at the HRU. Blood samples will be collected at -10, 0, 15, 30, 60, 90, and 120 min for measurement of glucose, insulin and C-peptide concentrations ⁷. Plasma samples will be drawn at baseline and throughout the MMT for measurement of additional hormones (such as leptin, ghrelin, thyroid hormones, and catecholamines) and free fatty acids (FFA) levels. Insulin and glucose will be used to calculate indexes of insulin sensitivity ⁷⁻⁹. Hormones, glucose and FFA will be correlated with PET measurements of brown fat at baseline and during the MMT. Approximately 60 mL of blood will be drawn at this visit.

HIC 2000030749

Participants will undergo whole body [¹¹C]MRB PET scan as described in visit 3. After the MMT, PET data will be acquired dynamically for 120 min using the Siemens mCT-X whole-body PET/CT scanner after an intravenous bolus dose of MRB (~20mCi).

The order of the PET scan visits 2 and 3 will be randomized.

PET and MSNA visits do not need to occur in sequence, i.e. PET scans can occur before or after the MSNA.

Measurement of Energy Intake: Hunger and fullness will be determined immediately before, during and after the PET scans with Visual Analog Scales (VAS).

Visit 4 – Sympathetic Nervous System Activity (SNSA) measurement Visit - Fasting

Two weeks after visit 3, participants will be asked to return for a separated visit for measurements of SNS activity at rest and fasting. This visit will be performed at the Pierce Laboratory ([name] laboratory). The participants will come in the morning (~9am) and will be asked to fast for 10-hour and to maintain their regular exercise routine. The following measurements will be obtained: MSNA, heart rate (HR), blood pressure (BP), electrocardiogram (EKG), and heart rate variability. The proposed procedures will be performed at fasting (baseline). Participants will be asked to maintain their regular exercise routine.

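### The mixed-meal power figures are for energy expenditure in low- versus high-BAT people, which the trial neither measures nor compares, so power for the meal objective is undocumented

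*Combined protocol and SAP*

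**What the plan says.** Section 6.4.2 (Sample Size Considerations) has a general opening statement, a fasting calculation and an MMT calculation. The MMT calculation takes postprandial whole-body energy expenditure per kg of fat-free mass from a cited study, "low-BAT (32 ± 2 kcal/day/kg FFM) and high-BAT (37 ± 2 kcal/day/kg FFM", and derives d=2.50. It then states "we will need 8 individuals (4 per group) determine EE differences between low- and high-BAT individuals" for 80% power, and "Increasing the power to 0.95 will increase the number of individuals to 12 (6 per group". It closes with an allowance of about 10% for microneurography failure and recruitment of 10 per group.

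The meal objective itself is secondary objective 3 in section 4.3: "To investigate NET CNS and peripheral SNS activity before and after a high carbohydrate mixed meal in lean and obese men and women". It is repeated in sections 5.2.2 and 6.5.2. Section 2.1.2 describes the comparison as MRB binding in response to a meal, obesity against normal BMI, with MSNA measured in the same conditions.

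In section 6.4.1 the primary endpoints are group differences in MRB binding and MSNA, and brain-periphery correlations. The list then reads "Secondary endpoints: Plasma hormone levels, heart rate, blood pressure, electrocardiogram (beat-to-beat". The analysis text adds: "Linear contrasts comparing differences between groups or different time points within a group will be estimated".

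**The concern.** A power statement is useful only if it refers to an outcome the trial measures and a comparison it will make. Here both are borrowed from another study. Energy expenditure is not NET binding or MSNA. A low- versus high-BAT split is not lean versus obese. A difference between two sets of people also says nothing about the SD of a within-person change from fasting to fed, which governs power for the meal objective.

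A reader who takes the MMT paragraph at face value will believe the meal question has 80% power with 4 per group and 95% with 6. If the meal comparison then comes out null, that figure invites the conclusion that no effect exists, when the design may simply be unable to see one of plausible size. The meal question is not marginal to the trial: it takes two of the four post-screening visits (3 and 5).

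**Working it through.** **1. Reproduce the plan's figure.** Inputs from section 6.4.2: means 32 and 37, SD 2 in both (the ± is read as an SD; the text does not label it). The plan states no alpha; two-sided 0.05 is assumed throughout.

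d = (37 − 32)/2 = 2.50. Power is from the noncentral t with 2n − 2 degrees of freedom and noncentrality d·√(n/2):

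- n = 4 per group: 83.6% (n = 3 gives 63.6%), so 4 is the minimum for 80%.
- n = 6 per group: 97.3% (n = 5 gives 93.2%), so 6 is the minimum for 95%.

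Both stated sample sizes reproduce.

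**2. Is the outcome in the trial?**

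- The visit schedules (sections 6.2, 6.3.1 and 6.3.5) list no energy-expenditure measurement.
- At the MMT visits in section 5.1, energy expenditure appears only to size the drink: "equal to 40% of daily energy expenditure, per ~16 ounces".
- The energy item at the MMT PET visit is appetite: "Measurement of Energy Intake: Hunger and fullness will be determined immediately before, during and after the PET scans".
- Energy expenditure is in neither endpoint list (Synopsis; sections 5.2 and 6.4.1).

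**3. Is the contrast in the trial?**

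- Enrolment is by BMI and sex (sections 5.3.1 and 5.3.2).
- The SUV cut of 1.25 separates BAT from WAT within a region of interest; it does not classify people.
- No low/high-BAT analysis is planned (sections 6.4.1, 6.5.1 and 6.5.2), and section 6.5.9 (Subsets and Covariates) is N/A.

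**4. Is there another MMT power figure?** No. The fasting calculation is a cross-sectional BAT DVR comparison (d=2.20). The opening 90% statement in section 6.4.2 names no meal outcome.

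**5. What can the sample detect on its own contrasts?** Evaluable numbers under the plan's 10% loss are 20 × 0.9 = 18 per BMI group and 10 × 0.9 = 9 per BMI-by-sex cell. The formulas, with effects in SDs of the fasting-to-fed change, are:

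- Paired change within a group: noncentrality δ√n, n − 1 df.
- Difference in change between two groups: noncentrality δ√(n/2), 2n − 2 df.

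Solving for 80% power:

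| n per group or cell | alpha | paired change | difference in change |
|---|---|---|---|
| 18 | 0.05 | 0.70 | 0.96 |
| 9 | 0.05 | 1.07 | 1.41 |
| 20 (no loss) | 0.05 | 0.66 | 0.91 |
| 10 (no loss) | 0.05 | 1.00 | 1.32 |
| 18 | 0.01 | 0.89 | 1.20 |
| 9 | 0.01 | 1.45 | 1.80 |

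The fed-state comparison of two groups has the same multipliers as the last column, but in SDs of the fed value.

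For scale, a difference in change of 0.8 SD has 64% power with 18 per group and 36% with 9 per cell.

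**6. Expected 95% confidence interval half-widths, in SDs of the change.**

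- Paired, t(0.975, n − 1)/√n: 2.110/√18 = 0.50; 2.306/√9 = 0.77.
- Between groups, t(0.975, 2n − 2)·√(2/n): 2.032 × √(2/18) = 0.68; 2.120 × √(2/9) = 1.00.

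**The case against.** The strongest reply is that little turns on this. The meal comparison is a secondary objective, the fasting calculation gives the same 6 per group, and the paragraph openly names energy expenditure as its quantity. All of that is true, and it is why the remedy is a change of wording and not of design. It does not make the 80% and 95% figures apply to the meal objective.

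It could also be said that low and high BAT stand in for obese and lean: section 2.1.2 reads the reduced binding in obese women as suggestive of less BAT. The protocol never makes that argument for the sample size, and energy expenditure would still be unmeasured. Section 5.1 does plan to correlate hormones, glucose and free fatty acids with brown-fat PET during the meal test. The energy-expenditure figure gives no power for that either.

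Three technical points stand as qualifications:

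- The detectable effects assume separate t-tests. A model pooling error over four cells of 9 (32 df, equal variances) would give 0.96 and 1.36 SD per cell instead of 1.07 and 1.41. The plan names a mixed model for MSNA but none for PET.
- A change score needs two usable visits. If the 10% loss struck each visit independently, 20 × 0.81 ≈ 16 per group would remain, and the detectable effects would be 0.75 and 1.02 SD.
- The microneurography sentence ends in 10 per group, whereas 6/0.9 rounds up to 7. If that sentence is kept, it should be tied to overall enrolment and not to the MMT calculation.

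**Conclusion.** The concern holds. The stated 80% and 95% power belong to an outcome and a comparison outside this trial, and the MMT objective has no power basis. The fault is relevance; the calculation is correct for what it describes.

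Whether power for the meal objective is adequate cannot be decided from the documents. They give no mean, SD or within-person correlation for meal-induced change in MRB binding or MSNA. Section 2.1.2 mentions greater BAT activation after a carbohydrate-rich meal, but without figures and not as a NET measure; its cold-exposure pilot concerns another stimulus. What can be said is conditional. With 18 per BMI group the design has 80% power for a change of 0.70 SD or a difference in change of 0.96 SD; within one sex, with 9 per cell, these become 1.07 and 1.41 SD. These figures rest on two-sided alpha 0.05, t-tests on the change, and 10% overall loss.

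**What to change.** In section 6.4.2, delete the energy-expenditure calculation with its 80% and 95% statements. Keep the allowance for microneurography failure, attached to the total enrolment of 40. Insert wording such as:

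> Assuming two-sided alpha 0.05, t-tests on the fasting-to-MMT change and 10% unusable data, the study has 80% power to detect, with 18 evaluable per BMI group, a change of 0.70 SD of the change within a group and a between-group difference in change of 0.96 SD; with 9 per BMI-by-sex cell, 1.07 SD and 1.41 SD. MMT effects will be reported with 95% confidence intervals.

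The expected half-widths can be added: about 0.50 SD (paired) and 0.68 SD (between groups) with 18 per group, and 0.77 SD and 1.00 SD with 9 per cell. If the sponsor plans a pooled model or expects loss at each visit, the figures should be recomputed on that basis and the assumption stated.

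The cost is protocol wording only, and a stated power that looks less favourable. Participants, visits, endpoints and sample size do not change, because the fasting BAT DVR calculation separately gives 6 per group.
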